6.2.5 Blinding

The RedCAP randomization module conceals the randomization sequence. Thus, prior to randomization, all study personnel will be blind to allocation. Upon randomization, follow-up research staff assessors will remain blinded to allocation. These staff include those performing follow-up interviews, test meals, body measurements, and insulin resistance. Additionally, raters of intervention administration fidelity/competence (Drs. [name] and [name] research groups, experts in MBI and CBT programs, respectively) will remain blinded to rating of the adolescent group intervention sessions, as well as raters of group cohesion. [name] and [name] will remain blind until the database is locked.

To protect the blind, the intervention arm allocation will be limited to the minimum number of study documents necessary to pragmatically operate the study. Research staff running follow-up assessments, as well as the expert raters and Drs. [name] and [name], will not have access to any study document that reveals the blind.

6.2.6 Follow-up Visits

There are two follow-ups for this study: a 6-week/post-treatment follow-up and a 1-year follow-up. The 6-week follow-up visit ideal window will be within 4 weeks of the last group session; the 6-week follow-up will be completed no longer than 8 weeks after the last session of the group intervention. The 1-year follow-up visit ideal window will be 12 months (-/+ 4 weeks) after the first group session; the 1-year follow-up will be completed no longer than 18 months after the first day of the group intervention.

The following assessments will take place at each follow-up:

6-week Follow-up Visit

The following assessments that were collected at baseline will be repeated:

- BMI: height/weight body measurements
- Physical: blood pressure/waist circumference (no Tanner/pubertal staging)
- Body composition: BodPod
- Depression symptoms: CES-D survey
- Suicidality/self-harm: K-SADS-COMP interview to assess suicidality and self-harm only since the group program started
- Insulin resistance: OGTT
- Hedonic eating: EDE interview, EES-C, REDS, and laboratory test meal and food preference questionnaire
- Stress reactivity: Trier Social Stress Test
- Therapeutic mechanisms: MAAS, FFMQ, BRIEF-Parent Version, Children's Automatic Thoughts Scale, and PES
- Medical health history: Medical health, including treatment history (e.g., new medications, initiation of counseling, etc.), will be updated
- At-home collection: Adolescents will re-wear ActiGraph assessment of physical activity and repeat home saliva collection

In addition to the repeat assessments, we also will conduct the following evaluations at the post-treatment/6-week follow-up interval:

- Adolescent focus groups: We will conduct adolescent focus groups with each MBI, CBT, and HealthEd group. This qualitative strand adds patient voice to this multisite intervention refinement and optimization phase, ensuring outcomes of a future, larger efficacy trial are meaningful, valuable, and helpful for adolescents.¹⁷² Trained moderators will facilitate small group discussions, using a mix of open-ended and targeted questions designed to engage adolescents and elicit emergent themes that may not have been captured through the quantitative strand.¹⁷³ Focus groups will cover adolescents' subjective experiences of: 1) enabling mechanisms, 2) stress/mood management, 3) negative aspects of interventions, 4) facilitators/barriers to home practice, and 5) perceptions of group cohesion/facilitator alliance.
- Parent acceptability: Parents will complete an adapted program acceptability questionnaire¹³¹ to assess parents' knowledge and monitoring of their adolescents' home practice assignments, as well as parents' perceptions of likeability, credibility, and perceived benefits to their teenagers' stress, mood, health behaviors, and physical health and T2D risk. In addition to structured questions, we also will include open-ended prompts to provide feedback on enablers/barriers to group participation and home practice.

1-year Follow-up Visit

The following assessments that were collected at baseline will be repeated:

- BMI: height/weight body measurements
- Physical/puberty: blood pressure/waist circumference/Tanner staging and self-reported puberty questionnaire
- Body composition: BodPod

- Depression symptoms: CES-D survey
- Suicidality/self-harm: K-SADS-COMP interview to assess suicidality and self-harm only since the last assessment
- Insulin resistance: OGTT
- Hedonic eating: EDE interview, EES-C, REDS, and laboratory test meal and food preferences questionnaire
- Stress reactivity: Trier Social Stress Test
- Therapeutic mechanisms: MAAS, FFMQ, BRIEF-Parent Version, Children's Automatic Thoughts Scale, and PES
- Medical health history: Medical health, including treatment history (e.g., new medications, initiation of counseling, etc.), will be updated
- At-home collection: Adolescents will re-wear ActiGraph assessment of physical activity and repeat home saliva collection

In addition, adolescents will report their degree of maintenance of techniques or application of knowledge learned during the intervention:

- Maintenance: Adolescents will report the degree to which they are using MBI, CBT techniques and/or application of HealthEd knowledge.

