Randomization procedure: Upon completion of all screening and baseline assessments, each eligible participant will be randomly assigned to either an MBI, CBT, or HealthEd group condition. A separate randomization sequence will be created for each site. Within site, we will create four strata by crossing sex and age group (12-14y, 15-17y) and we will use permuted blocks within each stratum to ensure the intervention group arms are balanced. A statistician in the Children's Hospital Colorado's Biostatistics Core, other than the study lead statistician ([name]), will create the computerized randomization sequence and enter the sequence into REDCap's randomization module. REDCap's randomization module conceals the randomization sequence. The lead research coordinator will be responsible for using the REDCap randomization module to carry out randomization of eligible participants.

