- iii. Medical and family history: A brief psychiatric and medical health history, including T2D, prediabetes, and gestational diabetes, of the participant and family will be conducted with a parent/guardian by a trained research staff member. Psychiatric history includes parent and teen report of any mental health diagnoses that could be exclusionary; if the family reports a current mental health diagnosis (e.g., anorexia nervosa, bipolar disorder, bulimia nervosa, conduct disorder, MDD with high acuity, obsessive compulsive disorder, panic disorder, posttraumatic stress disorder, psychosis, and substance/tobacco/alcohol use disorder), a psychologist will speak with the family for further assessment and follow-up/referrals (and exclusion), as indicated. Eligibility based upon at least one first- or second-degree relative will be determined, as well as medication status. As in our other studies,^{119,138} females will report whether they are or suspect that they could be pregnant. Pregnant females will not be included.
- iv. Psychopathology: The Schedule for Affective Disorders and Schizophrenia for School-Age Children (K-SADS) – Computerized Version¹³⁹ Suicidality and Self-Harm module will be administered to determine if adolescent girls and boys report depression acuity that, in the opinion of the study investigators, would warrant study exclusion and necessitate a referral for more intensive treatment. Any participant with current active suicidal ideation or self-harm, regardless of degree of mood concerns, will be referred for treatment (and excluded). If the screening visit is completed remotely, a parent or guardian will be asked to be in the home and accessible for the duration of the completion of the K-SADS to ensure access for communication of any safety concerns. Additionally, the interviewer will confirm the child's physical location prior to starting the interview. Written remote safety protocols have been developed in the event that suicidal ideation or other risks concerns arise.
- v. Physical exam/puberty staging: Physical exam, including puberty staging as well as review of vitals, blood pressure, and waist circumference, will be conducted to evaluate adolescent health status. Exam may take place during either the first or second screening visit based on participant and provider availability.

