Upon completion of all screening and baseline assessments, a research staff will notify the adolescent and their parent/guardian that they completed all screening and baseline assessments and are eligible. The ideal window is that screening/baseline assessments will occur within 12 weeks/3 months of the start of the intervention phase (first group session); we will allow for up to 6 months between screening/baseline and group initiation. In the event that more than 6 months transpires since the screening/baseline interval, all interested adolescents who appeared to be eligible or who had been determined to be eligible, will be invited to complete a re-screening, referring to a repeat of all screening/baseline assessments. Re-screening will only be offered if there is sufficient opportunity for the participant to take part in a subsequent intervention cohort (e.g., originally screened for cohort 1, but after >6 months, could be re-screened to be considered for participation in cohort 2). After all screening/baseline assessments are complete and prior to randomization, adolescents and parent/guardians will be asked to confirm their desire to continue to participate in the study. Adolescents and parents will each, independently report their preference for group condition (MBI, CBT, HealthEd, or no preference). Adolescents then will be randomly assigned to either a MBI, CBT, or HealthEd group using the RedCAP randomization module by the lead study coordinator. Date of randomization will be considered date of enrollment.

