7.3 Specification of Safety Parameters

The following key measures and corresponding parameters will guide risk/safety handling:

- i. Oral glucose tolerance testing (OGTT): OGTT is conducted at three time points during the course of the study, including screening/baseline, 6-week follow-up, and 1-year follow-up. If an adolescent has impaired fasting glucose (fasting glucose ≥ 100 mg/dL), impaired glucose tolerance (2-hour OGTT glucose ≥ 140 mg/dL), or with values potentially suggestive of T2D (fasting glucose ≥ 126 mg/dL or 2-hour OGTT glucose ≥ 200 mg/dL) based upon immediate glucose analysis (e.g., StatStrip), they and their parent/guardian will be notified and referred to the primary care physician for follow-up. Those adolescents with T2D at baseline will be excluded. Adolescents with impaired fasting glucose or impaired glucose tolerance will not be excluded, but they and their families will be notified at baseline as well as any follow-up assessment.
- ii. Medical history/physical exam: A medical history is conducted at baseline/screening and updated at the 6-week and 1-year follow-up. A review of physical health is conducted at all three of these intervals, with pubertal staging only at baseline/screening and repeated at 1-year if a physician/provider reported adolescent to be below tanner staging 5 at baseline. Any adolescent with a major medical problem or taking medications that could interfere with safety or validity, at baseline, will not be included. Any adolescent with a current exclusionary mental health diagnosis reported by parents and/or adolescents will not be included. Physicians/medical providers at each site will review medical histories during the follow-up interval and if any medical condition develops that was not present at baseline, will refer families for medical treatment, as indicated. Likewise, psychologists will refer families for psychological treatment, as indicated.
- iii. Schedule for Affective Disorders and Schizophrenia for School-Aged Youth – Computerized Version (KSADS-COMP) – Suicidality/self-harm module and mood monitoring: The KSADS-COMP semi-structured clinical interview – Suicidality and Self-harm Module is conducted at three time points during the course of the study, including screening/baseline, 6-week follow-up, and 1-year follow-up. Mood monitoring is carried

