7.4 Adverse Events and Serious Adverse Events

7.4.1 Adverse Events

An **adverse event** is defined as any unfavorable and unintended diagnosis, symptom, sign (including an abnormal laboratory finding), syndrome or disease which either occurs during the study, having been absent at baseline, or if present at baseline, appears to worsen. All adverse events will be recoded regardless of their relationship to the study intervention (i.e., study and non-study related adverse events, as well as expected and unexpected adverse events).

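### For participants who complete the 6-week interview, no K-SADS suicidality look-back covers the time between the baseline interview and the first group session

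*Combined protocol and SAP*

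**What the plan says.** Section 7.3 fixes the number of interviews: the "Self-harm Module is conducted at three time points during the course of the study, including screening/baseline, 6-week follow-up, and 1-year follow-up". Under section 6.2.2 the baseline interview is given at the first screening visit and decides exclusion on current active ideation or self-harm.

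Section 6.2.6 sets the look-back for each follow-up:

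- 6-week visit: "K-SADS-COMP interview to assess suicidality and self-harm only since the group program started"
- 1-year visit: "K-SADS-COMP interview to assess suicidality and self-harm only since the last assessment"

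On the time before the groups start, section 6.2.4 names 12 weeks (3 months) as the ideal interval from baseline to the first session, then adds that "we will allow for up to 6 months between screening/baseline and group initiation". A repeat of the baseline assessments is offered only beyond 6 months. Randomization falls inside this interval. Section 4.3 states: "Upon completion of all screening and baseline assessments, each eligible participant will be randomly assigned to either an MBI, CBT, or HealthEd group condition".

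Section 7.4.1 counts as an adverse event one "which either occurs during the study, having been absent at baseline", or one that worsens from baseline. Section 7.6 has potential adverse events reported to the monitoring committee by condition and site.

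**The concern.** The sample is selected for elevated depression symptoms. Section 7.2 expects some participants to develop suicidal ideation or behavior, and the K-SADS module is the only structured interview on the subject. Its three administrations do not join up. The first asks about the present, the second starts at session 1, and the third starts where the second ended. An episode that began and resolved after the baseline interview but before session 1 is asked about in none of them if the participant completes the 6-week visit.

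Part of that interval lies after randomization, and section 6.2.7 follows everyone randomized whether or not they take part in the groups. The weekly mood form in sections 7.2 and 7.3 is filled in at sessions and has no stated look-back, so an adolescent who never attends completes none. At stake is the completeness of structured suicidality data over a stretch that can be longer than the one the 6-week interview covers.

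**Working it through.** The plan states no figure for this, so the check lays the interview windows on one timeline.

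**Inputs**

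- Baseline to session 1: 12 weeks (ideal limit) or 6 months (allowed limit), section 6.2.4
- Intervention phase: 6 weeks, Précis
- Last session to 6-week visit: within 4 weeks (ideal) or at most 8 weeks (allowed), section 6.2.6

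Assumptions: 6 months = 26 weeks, and holiday shifts of sessions are ignored.

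**Formula**

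Uncovered share = (baseline to session 1) / (baseline to session 1 + intervention phase + last session to visit)

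**Results**

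| Case | Uncovered | Covered by 6-week interview | Total | Uncovered share |
|---|---|---|---|---|
| Upper end of ideal windows | 12 | 6 + 4 = 10 | 22 | 12/22 = 55% |
| Upper end of allowed windows | 26 | 6 + 8 = 14 | 40 | 26/40 = 65% |

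In weeks, uncovered to covered is 12/10 = 1.2 and 26/14 = 1.9.

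**Sensitivity**

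- Counting six weekly sessions as spanning 5 weeks gives 12/21 = 57% and 26/39 = 67%.
- A 12-week wait with the latest allowed visit gives 12/(12 + 6 + 8) = 12/26 = 46%.
- A shorter wait lowers the share further. These are upper-end figures, not expected values.
- It is not stated whether the 6 months run from visit 1, where the K-SADS is given, or from visit 2. If from visit 2, the gap could slightly exceed 6 months.

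**Does the 1-year interview recover the gap?** For a participant who had the 6-week interview, it does not, because its window opens there. For one who missed it, the last assessment can be read as baseline, and the gap is then covered.

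**How much lies after randomization?** No limit is given from randomization to session 1. That part exists but cannot be sized.

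**With a 6-week look-back to the last K-SADS**, the uncovered interval is 0 in both cases.

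**The case against.** The case on the other side has five parts.

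- **Other routes exist.** Section 7.4.1 records all adverse events whatever their cause. Section 7.2 asks participants to report changes in wellbeing at any time. Section 6.2.6 updates the medical history, including new medication and counseling, and section 7.3 has providers review it. Attenders are asked about ideation at each session, so ideation still present at session 1 can be picked up. This stands. A reader might infer that events before session 1 would be lost from the safety data, and the documents do not show that. None of these routes, however, is a structured suicidality interview with a stated look-back over the gap.
- **The adverse event definition is not contradicted.** This also stands. Section 7.4.1 says what counts as an event, while section 6.2.6 sets one instrument's recall period. The two start at different points, but that alone is not a contradiction.
- **Starting at session 1 isolates events during or after exposure.** That is a coherent aim, since nothing is delivered earlier. An onset date serves it equally well and keeps the events between randomization and session 1.
- **The size is easily overstated.** Dividing the 26-week limit by 5 weeks of sessions gives a ratio of about 5, but that pairs the longest wait with a visit on the day of the last session. Nor may the whole 6 months be charged to by-arm data, because arms do not exist before randomization.
- **Unseen documents may help.** Section 7.2 cites a detailed procedure for worsening mood, and section 7.6 a separate monitoring plan. Either might hold an onset date or a check before session 1. The look-back stated in the protocol would still need correcting.

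**Conclusion.** The point holds for participants who complete the 6-week interview. For them, the time from the baseline interview to session 1 lies outside every K-SADS look-back. It is 55% of the period from baseline to the 6-week interview at the upper end of the ideal windows and 65% at the allowed limit, given 26 weeks for 6 months and a 6-week intervention phase.

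A reader might extend this to all participants. The 1-year wording does not support that, because those who miss the 6-week visit may be covered at 1 year.

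The consequence is possible under-ascertainment, greatest in never-attenders who do complete the 6-week interview. Any effect on the comparison of arms is confined to the unsized part after randomization. No primary or secondary endpoint in section 8.5 depends on it. The change is worth making because it is cheap and concerns the main psychiatric safety measure.

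**What to change.** Reconcile the two look-back statements in section 6.2.6 so that consecutive K-SADS interviews leave no gap, with the 6-week look-back running from the last K-SADS interview. Record an onset date, if the form does not already do so, so that events can be tabulated separately as before randomization, between randomization and session 1, and after session 1. Referral and exclusion rules stay as they are.

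The cost is one phrase and at most one form field, with no added visit, instrument or staff. Recall at the 6-week visit lengthens from 10 to 22 weeks at the upper end of the ideal windows, and from 14 to 40 weeks at the allowed limit. For comparison, a 1-year interview held 52 weeks after session 1 already looks back 52 - 14 = 38 to 52 - 10 = 42 weeks in those two cases.

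Timing matters. Section 3.6 expected enrollment to finish in July 2023, and version 10.0 is dated 24 October 2023, so many 6-week interviews may already be complete. A change now would leave two recall windows in the data. If the interviews are done, state the gap when safety is reported by arm and carry the corrected wording into the planned efficacy trial, for which section 1.2 already foresees updated assessment protocols.

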6.2.7 Completion/Final Evaluation

The 1-year follow-up visit, including at-home collection evaluations, represents the participant's completion of the study and final evaluation. In line with the intent-to-treat principle, we will follow all participants who are enrolled/randomized regardless of their participation in the intervention phase. Adolescents who are eligible at baseline but who develop conditions that would have been exclusionary will continue to be studied unless there is a concern about safety and/or a significant concern about validity (e.g., female who becomes pregnant and is pregnant or nursing at the time of the 6-week or 1-year follow-up evaluation). In samples of adolescents with overweight/obesity, family history of T2D, and elevated depression symptoms, it is anticipated that some adolescents will develop T2D and MDD. Safety assessments are in place, as in our other trials, and are addressed in this protocol, **section 7**. At completion of the 1-year follow-up/study endpoint, we will give study participants a letter of appreciation for their participation. Because we are working with at-risk adolescents in this study, we will provide a site-specific study mental health referral list to all participants at the conclusion of the study.

Upon initiation of the 1-year follow-ups for the study, we will conduct personnel focus groups (e.g., research coordinators, research assistants, intervention facilitators) to qualitatively evaluate the protocol. These focus groups will cover personnel's subjective experiences of: 1) enabling mechanisms, 2) negative aspects, and 3) protocol barriers. Information gleaned from these focus groups will inform modifications to optimize all aspects of the protocol for a future larger scale multisite efficacy trial.

7. RISK ASSESSMENTS

7.1 Risks

The risks associated with participation in the proposed study are consistent with IRB definitions of minimal risk. Participants and their parents/guardians will be informed in detail of all potential risks during the informed consent and assent process. We anticipate the follow risks:

- i. Physical examination: Physical examination by a licensed medical provider, including a physician or advanced practice provider, will be performed in a private examination room. Although appropriate measures will be taken to protect privacy, some adolescents may find this embarrassing.
- ii. Phlebotomy: We will draw a blood sample in a fasted state and two-hours after glucola administration. We will minimize the pain of blood drawing by offering the participant numbing cream prior to the blood draw. Blood will be drawn by venipuncture, but finger prick for point-of-care glucose assessment will be offered if blood cannot be obtained by venipuncture. Discomforts are common, but minor. In about one in 10 cases a small amount of bleeding under the skin will produce a bruise (uncommon risk). The risk of a blood clot forming in the vein is about one in 100, while the risk of infection or significant blood loss is one in 1000 (rare, but serious). Amount of blood withdrawal (no more than 3 tablespoons at the screening, and 3 tablespoons at each of the 2 follow-up appointments: 6-week and 1-year) is well below the NIH and pediatric IRB guidelines for a safe amount of blood withdrawal.
- iii. ActiGraph: This small device to measure moderate-to-vigorous physical activity and sedentary time will be worn on the hip for 7 consecutive days at the baseline period and again at the 6-week and 1-year follow-up intervals. Aside from the inconvenience of wearing the device and removing it during water-based activities (e.g., swimming), as well as the time required to complete the accompanying log to record activity, there is no risk involved with these devices.
- iv. Air displacement plethysmography (BodPod): Body fat and fat-free mass measurements by BodPod involve no risk and are not painful. It is possible that some participants may feel slightly claustrophobic because the BodPod requires the occupation of a small space for a short period of time. Participants also must wear tight-fitting clothing, such as a bathing suit, for the test. Participants can always communicate with the experimenter during the test. Any individual who is uncomfortable may stop the test at any time.
- v. Salivary samples: Saliva samples entail no risk but may be inconvenient.
- vi. Psychological questionnaires, interviews, and focus group: Psychological testing involves no risk but may cause inconvenience because of the time required for testing. It also may cause slight discomfort if the wording of some questions makes the subject uncomfortable. The scales and interviews used are well-validated instruments designed to seek information without undue embarrassment to the participants. Qualitative focus group queries will be prepared with the guidance of [name] (Co-I), a psychologist and qualitative expert, and administrators will be thoroughly trained in their proper, standard administration. For all quantitative and qualitative measures, participants are not required to answer a question if it makes them uncomfortable. Psychological questionnaires will be administered by trained research staff. Psychological interviews will be conducted by a psychologist or trained post-doctoral fellow, graduate student, or research coordinator.
- vii. Laboratory test meals: Food ingestion under controlled conditions involves no risk and is not expected to cause any participant discomfort. Participants who report food allergies to items on the laboratory test meal will not participate in this assessment for safety; based upon our prior implementation of this meal paradigm with 1,000s of youth, the vast majority (>99%) are not allergic and report high liking of the foods served. Research staff who will be preparing and measuring food for the laboratory

test meals will have completed food safety training that focuses upon safe food handling, proper temperatures, hand washing, and using gloves for handling foods. Staff also will be trained on the weighing/processing of foods for controlled feeding studies to ensure consistency in the method and presentation within and across the study sites.

- viii. Trier Social Stress Test (TSST): The TSST has been used in multiple vulnerable populations, including children and adolescents, the elderly, and pregnant women. While it may make participants temporarily nervous or uncomfortable, the TSST is designed to specifically elicit the physiological response system. Performing this task may cause some temporary emotional distress. Typically, this distress does not last long. The amount of physiological arousal that the TSST generally elicits is roughly comparable to mild physical exertion. Participants are told ahead of the task that they have the right to stop the task at any point should they wish. If there is evidence of severe distress, researchers are trained to stop the task. All participants are debriefed after each visit in which the TSST is administered.
- ix. Group participation: In the course of MBI, CBT, and HealthEd, issues arise that may be uncomfortable or stressful for some participants. Based upon the participant's level of comfort and relevance of the concern to the group process, such issues may be discussed in the group. In querying adolescents about their psychological functioning, serious psychiatric disturbances may be uncovered. In addition, topics that may be personally sensitive will be discussed in group. Emotional distress is typically expected and often an important component necessary to make the changes required for improvements in mood or stress. There also may be times of conflict between group members. While stress and interpersonal conflict are emotionally difficult experiences and may cause distress for participants, they are often part of the process of making changes. The goal of the group facilitators and the group as a unit is to support each participant through stressful periods in order to reduce depressive symptoms and improve mood. Groups will be led by a psychologist, who will be fully trained in the programs, and they will receive weekly supervision from [name] (MBI) and [name] (CBT, HealthEd).

